11.4 Deviations, serious breaches and other reporting obligations

The responsible investigator and/or any involved service provider shall, without delay, report to the sponsor any suspected serious breaches from the trial protocol, the CTR, ICH-GCP and other regulations that are likely to affect the safety, rights of the subjects and/or the data reliability and robustness to a significant degree. The sponsor should assess the suspected serious breach, the consequences of the deviations and without undue delay, but no later than 7 days (from knowledge), report these to the Competent Authorities via CTIS.

Other unexpected events that may affect the benefit/risk relationship for the clinical trial must be reported via CTIS without undue delay, but no later than 15 days after the sponsor becomes aware of the event.

Minor deviations that do not affect subjects' integrity or safety, nor significantly affect the trial's scientific value, are documented in the trial documentation of the principal investigator and the sponsor and appropriate measures shall be taken. The deviations, including minor deviations, must be recorded in the clinical trial report.

11.5 Audits and inspections

The purpose of an audit or inspection is to review trial-related activities and documents systematically and independently, to determine whether these activities were performed, registered, analysed and reported correctly according to the protocol, ICH-GCP and applicable regulations.

Authorized representatives for the sponsor and Competent Authorities (CA) may carry out audits or inspections at the trial site, including source data verification. The investigator must ensure that all source documents are available for audits and inspections.

12 ETHICS

12.1 Compliance to the protocol, ICH-GCP and regulations

The trial will be performed in compliance with this clinical trial protocol, the EU regulation on clinical trials on medicinal products for human use (536/2014), the Declaration of Helsinki, ICH-GCP (Good Clinical Practice), and current national regulations governing this clinical trial. This is to ensure the safety and integrity of the trial subjects as well as the quality of the data collected

12.2 Ethical review of the trial

The final protocol for clinical trials on medicinal products must be approved, as a part of the application for a permit for clinical trials via CTIS, by the Competent Authorities, before the trial can be conducted. The authorities must be informed via CTIS of any changes in the trial protocol in accordance with current requirements.

12.3 Procedure for obtaining informed consent

The principal investigator at each site shall ensure that the subject is given full and adequate oral and written information about the trial, its purpose, any risks and benefits as well as inclusion and exclusion criteria. Subjects must also be informed that they are free to discontinue their participation in the trial at any time without having to provide a reason. Subjects should be given the opportunity to ask questions and be allowed time to consider the provided information. If the subject chooses to participate, both the subject and the investigator shall sign the informed consent form. A copy of the subject information as well as the informed consent form shall be provided to the subject. The subject's signed and dated informed consent must be obtained before any trial-specific activity is performed. Each subject who participates in the trial will be identified by a subject number on a subject identification list. The subject agrees that monitors, auditors, and inspectors may have access to the subject's medical records and other source data. If new information is added to the trial, the subject has the right to reconsider whether he/she will continue their participation.

12.4 Data protection

In the information provided to subjects, subjects will be fully informed about how their trial data will be collected, used and disclosed. The content of the informed consent form complies with relevant integrity and data protection legislation. The subject information and the informed consent form will explain how trial data are stored to maintain confidentiality in accordance with national data legislation. All information processed by the sponsor will be pseudonymized only identifiable with the study id.

The informed consent form will also explain that for verification of the data, representatives delegated by the sponsor, as well as relevant authorities, may require access to parts of medical records or trial records that are relevant to the trial, including the subject's medical history.

12.5 Insurances

All subjects participating in the trial are covered by the Swedish Patient Insurance (patientförsäkringen) through Regionernas Ömsesidiga Försäkringsbolag, LÖF.

13 SUBSTANTIAL CHANGES TO THE STUDY

Substantial changes to the signed clinical trial protocol are only possible through approved protocol amendments.

In the event that substantial changes to the protocol which may affect the safety, rights of subjects or the reliability and robustness of data generated need to be implemented during the course of the trial, permission from the relevant authority via application in CTIS should be obtained before implementing the change. This includes the addition of a new trial site or a change of the principal investigator at the trial site.

Non-substantial amendments are entered into the CTIS in the next substantial amendment application concerning the same part. If the non-substantial change is relevant to the Authority's oversight (e.g. contact details), the CTIS should be updated on an ongoing basis.

14 COLLECTION, HANDLING AND ARCHIVING OF DATA

14.1 Case Report Form - eCRF

The REDCap system will be used as electronic clinical record form (CRF) (<https://www.project-redcap.org/>). All data is kept within Region Västra Götalands firewall. Two-factor authentication is used, and data is securely stored according to rules and regulations for class III data. Data will be entered prospectively unless the patient is included after completed neoadjuvant treatment, when data up to that visit will be entered retrospectively. Data will be entered at the following time points and details on required information is presented in Table 1. Details on data entered in the CRF is presented in appendix.

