4.3 Primary endpoint

Primary variable: clinical complete response rate. Measured as the ratio of patients with a non-operative approach at onset that after evaluation by a combination of MRI, clinical and endoscopic examination have a clinical complete response at 1 year.

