566 before being referred to the hospital including in the clinical trial. A treatment plan will be set,
567 and the patient will sign informed consent and can then either receive the treatment according
568 to the study protocol at the hospital participating in the clinical trial or in a decentralized
569 manner.

570 All clinical information entered into CRFs will be entered by the hospitals participating in the
571 clinical trial regardless of decentralized process or not.

572 Individuals who do not wish to enter the study will be offered standard treatment according to
573 the Swedish National Treatment Guidelines for Colorectal Cancer, i.e. TME surgery. The
574 experimental organ saving treatment is not offered outside a study setting unless unfit for
575 primary TME surgery.

576 Details of all participants approached about the trial will be recorded on the Participant
577 Screening Log. The following data will be recorded:

- 578 1. Sex
- 579 2. Age
- 580 3. Clinical TNM according to TNM v8
- 581 4. Planned oncologic and surgical treatment

582 In addition – all patients treated at the participating hospitals are registered in the Swedish
583 ColoRectal Cancer Registry (SCRCR). If necessary, missing information will be retrieved
584 (sex, age and clinical TNM stage, type of surgery performed and recurrence data) on non-
585 included patients using the SCRCR

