8 METHODS FOR MEASUREMENT OF ENDPOINTS FOR CLINICAL EFFICACY AND SAFETY

8.1 Methods for measurement of endpoints for clinical efficiency

8.1.1 Primary endpoint

Primary variable: clinical complete response rate. Measured as the ratio of patients with a non-operative approach at onset that after evaluation by a combination of MRI, clinical and endoscopic examination have a clinical complete response at 1 year.

Definition of clinical complete response (cCR)

1. No suspicious metastatic lymph nodes or evidence of remaining tumour on MRI. In a majority a complete response on MRI will be seen as areas of homogeneous fibrosis. Absence of any remaining pathological tissue is seen in a minority of cases.
2. Endoscopic examination with white light. Presence of light/white mucosa or scar, telangiectasia. Presence of fibrosis and oedema.
3. No palpable tumour on clinical examination if the tumour was palpable initially.

Definition of near clinical complete response – possible to re-examine again after four weeks

1. The majority of the tumour is converted to fibrosis with homogeneous low signal intensity on T2-weighted images with minor areas of impeded diffusion on high b-value DWI.
2. Using white light endoscopy with phosphate enema (or comparable) bowel preparation any one of the following are encountered:
 - a. Residual mucosal irregularity
 - b. Residual flat ulcer
 - c. Submucosal irregularity or swelling

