9.7 Procedures in case of emergencies, overdose or pregnancy

Medication errors, pregnancy and use of other medicinal products than those specified in the protocol, including misuse and abuse of the investigational medicinal product, shall be subject to the same reporting obligations as adverse reactions.

If an unforeseen event is likely to have a serious impact on the benefit/risk relationship of the trial, the sponsor and investigator should take appropriate Urgent Safety Measures (USM) necessary to protect the subjects. Examples of such measures are to temporarily halt the clinical trial or to introduce supplementary monitoring measures. The sponsor should, via CTIS, inform the concerned Member States about the event and the measures taken. Notification must be made as soon as possible, but no later than seven days after the measures have been taken.

949 If a subject or partner to a subject who participates in a clinical trial, becomes pregnant, this
950 person will be followed up until the birth has taken place. If the foetus/child has any
951 congenital malformation, this must be reported as a serious adverse event (SAE).

952 **10 STATISTICS**

953 **10.1 Analysis population and statistical analyses including sample size** 954 **calculations**

955 A statistical analysis plan will be developed for the primary endpoint before start of inclusion and for all secondary endpoints before analysis. Descriptive statistical methods will be used to present data, and assuming a non-normally distributed data non-parametric statistics will be used.

956 Using a sample size of 82, the critical number of successes is 49. If 49 or more patients achieving complete response at one year, the null hypothesis will be rejected at alpha 0.05. Conversely, if 34 or more patients have negative response, then the null hypothesis cannot be rejected. If at any time 49 complete responses or 34 negative responses are observed, rejection/failure to reject is known with 100% certainty. However, we plan to include patients until the randomized controlled trial STAR-TREC continues follow-up.

957 **11 QUALITY CONTROL AND QUALITY ASSURANCE**

958 **11.1 Quality Assurance and Sponsor oversight**

959 The sponsor's quality-related work is based on a risk analysis of the trial as a whole: design,
960 conduct, data collection, evaluation, reporting and archiving. The sponsor will perform quality

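### Section 14.1 provides for inclusion after neoadjuvant treatment is complete, contradicting the entry sections and leaving the one-year cCR rate open to upward bias

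*Protocol*

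**What the plan says.** Section 14.1 of the protocol describes the electronic CRF and says: "Data will be entered prospectively unless the patient is included after completed neoadjuvant treatment, when data up to that visit will be entered retrospectively". The other places that govern entry are these:

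- **Section 6.3:** the patient signs consent and then receives treatment, either at the participating hospital or decentralized.
- **Section 5.2, Table 1:** written consent is marked at screening only.
- **Section 5.1, list of CRF time points:** inclusion is item 1 and start of neoadjuvant treatment is item 2.
- **Synopsis and section 6.2:** previous pelvic radiotherapy is an exclusion criterion.
- **Synopsis and section 5.1:** the trial is described as prospective.

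The primary endpoint (4.3 and 8.1.1) is the "ratio of patients with a non-operative approach at onset" who have a clinical complete response at one year. Section 5.1 places the first response assessment 6-8 weeks after the end of chemoradiotherapy. Section 10.1 fixes the decision rule: "Using a sample size of 82, the critical number of successes is 49", and "If 49 or more patients achieving complete response at one year, the null hypothesis will be rejected at alpha 0.05".

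**The concern.** The sentence in 14.1 is about when a patient is included, not only about when data are typed in. It describes a route into the trial after treatment and tells sites how to fill the CRF for patients who take it. A site could follow this sentence or the entry sections, and the protocol does not say which prevails.

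The route matters because the primary endpoint is a single-arm proportion tested against a fixed rate, with no concurrent group to absorb selection. Under section 5.1, complete responders go on to surveillance and patients without a complete response go to TME surgery. If some patients enter after the first assessment, those who responded are the more natural candidates. They would add to the numerator, while comparable patients who failed would be absent from the denominator.

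Toxicity data are also affected. Anyone entering by this route has, by definition, completed treatment. The weekly toxicity review in 9.2.2 and the 72-hour adverse event entry in 9.3.1 cannot be met prospectively for them.

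**Working it through.** **Inputs from the protocol.** n = 82 and critical value r = 49 (10.1); alpha 0.05, sidedness not stated (10.1); null rate 50%, inferred from the objective in section 4.0 because 10.1 does not name it.

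**Step 1: reproduce the plan's rule.** With X ~ Binomial(82, 0.5):

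- P(X ≥ 48) = 0.0753
- P(X ≥ 49) = 0.0485

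So 49 is the smallest count with one-sided alpha at or below 0.05. The rule is reproduced as a one-sided test of 50%. Doubling the tail at 49 gives 0.0970, so a two-sided 0.05 test does not yield 49. The failure count also agrees: 82 − 49 + 1 = 34.

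**Step 2: add late entrants.** Let m of the 82 patients enter after treatment with one-year response rate q, and let the other 82 − m have the null rate of 50%. The total number of successes is Binomial(82 − m, 0.5) + Binomial(m, q), and the type I error is the probability that this total is at least 49. Neither m nor q is in the documents; both are assumptions, so a range is shown.

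| m (share of 82) | q = 60% | q = 67% | q = 85% | q = 95% |
|---|---|---|---|---|
| 0 | 0.0485 | 0.0485 | 0.0485 | 0.0485 |
| 4 (5%) | 0.058 | 0.065 | 0.086 | 0.099 |
| 8 (10%) | 0.069 | 0.085 | 0.144 | 0.185 |
| 16 (20%) | 0.095 | 0.140 | 0.330 | 0.472 |

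For example, with m = 8 and q = 85% the expected number of successes is 74 × 0.5 + 8 × 0.85 = 43.8, against 41 without late entry.

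**Step 3: cross-check with a selection model.** Let a share f enter late, and let one-year failures enter late with probability k relative to responders. At true rate p the observed rate is (1 − f)p + f·p/(p + k(1 − p)). Take p = 0.5:

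- f = 10%, k = 0.5: 0.9 × 0.5 + 0.1 × 0.667 = 51.7%, type I error 0.087.
- f = 10%, k = 0 (only responders enter late): 55.0%, type I error 0.226.
- f = 20%, k = 0.5: 53.3%, type I error 0.146.
- f = 20%, k = 0: 60.0%, type I error 0.566.
- k = 1 (entry unrelated to outcome) or f = 0: 50%, type I error 0.0485.

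The two models agree where they overlap: k = 0.5 corresponds to q = 67%. The inflation comes from selection; late entry unrelated to response leaves the error rate unchanged.

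**The case against.** The strongest reply is that 14.1 governs data entry, not eligibility, and that the entry sections already close the door. Read literally, the exclusion of previous pelvic radiotherapy makes a patient who has completed chemoradiotherapy ineligible. Section 6.3 also allows decentralized treatment after consent, with CRFs completed only by the participating hospitals. The clause may therefore have been meant for patients who consented first, were treated elsewhere and reached the CRF late. That reading is possible, but the sentence speaks of the patient being included after treatment, and nothing else confines it. The contrary sections show that the text must be reconciled; they do not withdraw the exception.

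A second reply is that the analysis plan promised in 10.1, which is not shown, may say how late entrants count. It may. Who enters is still a protocol matter, and an analysis plan can set late entrants aside only if they are identified.

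Four stronger readings are tempting and are not supported:

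- *That the rate is biased.* The documents do not show that anyone will enter late or that such entry would be selective. A patient included after chemoradiotherapy but before the 6-8 week assessment has no known response. The screening log and national registry (6.3) might reveal selection, though they would not correct the estimate.
- *That late entry breaches 12.3.* That section says: "The subject's signed and dated informed consent must be obtained before any trial-specific activity is performed". Treatment given outside the trial before consent is not clearly a trial-specific activity. The relevant contrary text is 6.3.
- *That it contradicts the endpoint definition.* A late entrant who was treated for organ preservation also had a non-operative approach at onset. The definition fails to exclude late entrants; it does not conflict with them.
- *That late entrants would mostly be unfit for TME.* Section 6.3 says the "experimental organ saving treatment is not offered outside a study setting unless unfit for" primary TME surgery. That narrows the pool of already treated patients. But the synopsis requires TME to be judged reasonable and feasible, so unfit patients would fail eligibility.

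**Conclusion.** The point stands as an internal contradiction with a consequence for the primary endpoint. Section 14.1 provides for inclusion after treatment; sections 5.1, 5.2, 6.2 and 6.3 and the synopsis point the other way; and the endpoint wording would count such patients. If the exception is used, entry can depend on a known response and the one-year rate is open to upward bias.

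The size is unknown. Under the stated assumptions (50% null, one-sided rule of 49 of 82, remaining patients at 50%), the type I error moves from 0.0485 to about 0.07 to 0.18 with 8 late entrants at 60% to 95%, and to about 0.14 to 0.47 with 16 at 67% to 95%. With few or weakly selected late entrants the effect is small: 4 at 60% gives 0.058. Upward is the expected direction because responders stay under surveillance while the others go to surgery. The rule has little slack, since a threshold one success lower would already give 0.075.

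**What to change.** Reconcile the passages before recruitment. Delete the exception in 14.1 and state in 6.3 that consent and central registration, using the telephone registration already described in 14.2, take place before the first radiotherapy fraction. With 82 patients registered this way, the 49-of-82 rule keeps its one-sided error of 0.0485.

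If the clause was meant only for delayed data entry on patients who consented before decentralized treatment, reword it to say that.

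If late entrants are to be kept for other reasons, reconcile this with the pelvic radiotherapy exclusion, flag them in the CRF with the date of inclusion relative to treatment and to the first response assessment, leave them out of the primary-endpoint denominator, and report them separately, including their safety data.

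The cost is a sentence or two in 14.1 and 6.3, plus a statement of the primary-endpoint denominator if late entrants are kept. A few patients may be lost from the primary set.

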14.2 Data collection

All clinical data at inclusion, during and after neoadjuvant treatment, during surgery, during postoperative hospital stay and at yearly follow-ups will be entered into the REDCap CRF. At inclusion the study centre at SSORG, Sahlgrenska University Hospital will receive a phone call and register the patient to ascertain that all patients are registered properly.

After this all registration will be performed using a study number, not the personal identification number. The personal identification number and the study number will be kept either in a locked storage or at in a password protected and secure SharePoint document.

The postoperative questionnaires will be administered by the study secretariat at SSORG.

All data will be kept within University of Gothenburg and Sahlgrenska University Hospital IT systems using inherent security systems.

A logistic database with complete patient ID will be used, kept within a separate IT-system from the result database with all study information. Security measures will include one to maximum two users of this database, with unique usernames and personal login, as well as automatic throw-out.

The result database, based on trial number and without patient ID, will be kept within another IT system than the logistic database. The database will be kept on a server with automatic backup and will be registered with "integritetsskyddsombudet" for Sahlgrenska University Hospital.

14.3 Data management plan

A data management plan (DMP) based on the Swedish National Data Service (SND) checklist has been drawn up and will be continuously revised during the project. The plan covers all handling of data from project planning, through collection, analysis, and archiving.

The project has a designated data manager who work with storing and validating of data in the project. To uphold data security and integrity of study participants the routines of Västra Götaland Region and University of Gothenburg guidelines for handling sensitive data are followed.

Data in this project will contain information concerning health and is thereby classified as sensitive personal data by General Data Protection Regulation (GDPR). The processing of the

1105 sensitive data for scientific research purposes in this project will be according to GDPR article
1106 9 with lawful basis of public interest article 6e. The organisations that act as data controller
1107 for this project is Sahlgrenska University Hospital and University of Gothenburg.

1108 Confidentiality is identified as grade III and will thereby be protected by strong authentication
1109 when stored and encryption when transferred.

1110 Integrity is identified as grade III and will be protected against unintentional and unauthorised
1111 alteration. Routines for data to be regularly backed up as well as logging of alteration will be
1112 in place.

1113 Availability is identified as grade II and should be accessible at most hours and is established
1114 by stable and well tested IT-infrastructure.

1115 All data is pseudonymised and the key is stored in a separate secure server system not
1116 containing any study data.

1117 Clinical data will be entered directly in an electronic clinical record (CRF) by each
1118 participating centre through the REDCap web interface (<https://www.project-redcap.org/>).
1119 Data collected via REDCap will be stored directly on a server within the Västra Götaland
1120 Region firewall and is accessed through a two-factor authentication. Data can be accessed and
1121 retrieved from the data base only with the authorization by the principal investigator.

1122 Patient-reported outcomes will be retrieved by questionnaires. The study secretariate has well
1123 built-up infrastructure as well as experiences of handling sensitive and confidential data from
1124 randomised clinical trials. The logistics database with contact information on study
1125 participants is password protected. Accesses is given only to personnel who work in direct
1126 contact with participants for retrieving questionnaire during the study follow up period.

1127 Radiological and radiotherapy data will be analysed, stored, and processed according to
1128 regulation. The infrastructure used will either be within the Sahlgrenska University Hospital
1129 or by an external infrastructure explicitly for research purpose. In the latter case a data
1130 processor agreement will be established.

1131 Blood samples and biopsies will be marked only with study code and stored in biobank
1132 according to regulation. Data for the translation sub study will be analysed, stored, and
1133 processed according to the routines and infrastructure at Core Facilities at Sahlgrenska
1134 Academy, University of Gothenburg.

1135 Access to data will be given only for those who will actively work with data. Access to data
1136 for researchers and statisticians will be restricted to the data need for each analysis. Data
1137 manager will have access to all data retrieved by the study secretariate, as well as data in each
1138 analysis used for publication. Only the principal investigator group will have full access to all
1139 collected data in the project.

1140 If any data is to be processed outside of the data controller organisations a data processor
1141 agreement will be established to ensure that GDPR is followed.

1142 Any physical data containing personal information (e.g. paper questionnaires, consent forms)
1143 will be stored in locked rooms in buildings accessed only by authorised personal within the
1144 Sahlgrenska University Hospital.

1145 All participants will be informed on how data are managed and their rights according to
1146 GDPR before entering the study.

1147 **15 NOTIFICATIONS OF TRIAL COMPLETION, REPORTING AND** 1148 **PUBLICATION**

1149 End of recruitment of subjects and end of the trial is reported in CTIS, within 15 days. Within
1150 one year of trial completion a summary of the clinical trial results must be reported in CTIS,
1151 including a summary for lay people. In addition, a full clinical trial report with individual data
1152 is to be completed and archived in the trial master file by sponsor and in the investigator-site
1153 files at each site.

1154 The trial will be published after completion of the inclusion and completion of follow-up of
